## **Introduction**

This double-blinded, translational, human subject study will test the hypothesis that postmenopausal women, subjected to a daily 10-minute treatment of LMMS (low magnitude mechanical stimulation) for one year, will show an improvement in trabecular and cortical stiffness and failure strength at the tibia, along with a reduction in vertebral marrow adiposity relative to their placebo-treated peers. The intervention and measurement protocols pose minimal risk to participants.

## **Abstract**

We propose to evaluate the hypothesis that LMMS applied to postmenopausal women ages 45-65 improves the bone's mechanical integrity while lowering marrow adiposity. Specific Aims are: 1) We will optimize an integrated imaging protocol for high-resolution structural MR imaging of the distal tibia and spectroscopic imaging-based quantification of bone marrow composition in the lumbar vertebrae; 2) We will further develop and validate micro-finite-element (FE) analysis for quantitative assessment of trabecular and cortical bone stiffness and failure load from high-resolution MR images of the distal tibia, and 3) We will apply the methodology of Aims 1 and 2 in a double-blinded, randomized, placebo-controlled study to a cohort of 64 healthy postmenopausal women in the age range of 45-65 years, studied at baseline and 12 months after having been subjected to 10 minutes daily of either 30 Hz/0.3g stimulation or placebo treatment, monitored rigorously via electronic feedback.

## **Overall objectives**

We hypothesize that relative to placebo, LMMS treatment will result in: 1) increased trabecular and cortical stiffness and failure strength assessed at the distal tibia by MR image-based FE modeling; 2) increased BMD at the two peripheral sites measured by pQCT, and DXA of the spine and hip, and 3) reduced vertebral marrow adiposity, which will be reciprocally related to measures of BMD and strength.

## **Primary outcome variable(s)**

Increased trabecular and cortical stiffness and failure strength, assessed at the distal tibia by MR image-based FE modeling.

## **Secondary outcome variable(s)**

Increased BMD at the two peripheral sites measured by pQCT and DXA of the spine and hip.

## **Background**

Weight bearing exercise has an osteogenic effect by reducing bone resorption and enhancing bone formation. During the past several years a number of articles have appeared demonstrating that low magnitude mechanical stimulation (LMMS) is osteogenic in animals and also in humans. The mechanobiology underlying these phenomena is beginning to emerge in terms of expression of genes stimulated by the action of the vibrations to which osteocytes are subjected. If successful, LMMS treatment, a non-pharmacologic intervention, could prevent bone loss and potentially stimulate bone formation resulting in increased bone strength and reduced fracture susceptibility in subjects at risk of developing osteoporosis. The proposed project focuses directly on measures of strength by evaluating the therapeutic response in terms of magnetic resonance (MR) image-based micro finite-element (FE) assessment of bone stiffness and failure strength, along with quantifying treatment-induced changes in marrow adiposity, as part of a single, integrated examination, conducted at baseline and 12 months of treatment in a double-blinded, randomized, placebo-controlled study of postmenopausal women. Special consideration will be given to compliance, which will be enhanced by an electronic feedback system.

## **Study phase**

Phase II

## **Study design**

Double blinded, randomized, placebo-controlled.

## **Study duration**

Estimated length of time for enrollment: 2 years

Length of time of subject participation: 1 year

## **Resources necessary for human research protection**

All research staff involved with this study are experienced performing MRI studies of this type and all have completed the required training in human subjects research protection. The DXA and pQCT studies will take place in The Nutrition and Growth Lab at Children's Hospital of Philadelphia. The Nutrition and Growth Lab is used for many of the studies involving DXA and pQCT at the University of Pennsylvania. The MRI research facility at the University of Pennsylvania has dedicated scanners devoted to various research projects. Subjects will be recruited from a database of previous study participants as well as with outreach efforts to the University and general community via advertisements, letters and notices.

## **Target population**

Post-menopausal female subjects ages 45-65 years who have a history of amenorrhea for a minimum of 24 months and a serum FSH of 25 or greater.

## **Subjects randomized by Penn researchers**

83 (to reach final sample of 64 completers)

## **Subjects enrolled by collaborating researchers**

0

## **Accrual**

Subjects will be recruited from a database of previous study participants as well as with outreach efforts to the university and general community via advertisements, letters and notices. These methods have been successful in prior clinical trials.

## **Key inclusion criteria**

Females, ages 45-65 years in post-menopause, as defined by a history of amenorrhea for a minimum of 24 months and a serum FSH concentration of 25 mIU/mL and negative pregnancy test

## **Key exclusion criteria**

Current and prior use of medications known to affect bone (e.g. bisphosphonates, calcitonin, selective estrogen receptor modulators, denosumab, diphenylhydantoin, or glucocorticoids) may be considered for exclusion, bone mineral density T score of less than -2.5 and greater than +2, vitamin D level less than 12 ng/ml, BMI of greater than 32, current alcohol or drug abuse (more than 3 alcoholic beverages per day or current use of illicit drugs or prescription medications), uncontrolled or untreated cardiac or pulmonary disease, liver disease (history of hepatitis or ALT or AST greater than 2x ULN), renal disease (history of renal disease or serum creatinine greater than 2x ULN), diabetes, Pacemaker or metallic implants (considered contraindicated to MR scanning).

## **Vulnerable populations**

The following populations are not included in this research study: children, pregnant women, prisoners.

## **Subject recruitment**

Subjects will be recruited from a database of previous study participants as well as with outreach efforts to the university and general community via advertisements, letters and notices. These methods have been successful in prior clinical trials. Additionally, we will use the Penn Clinical Data Warehouse's (Penn Data Store) services.

## **Study procedures**

Screening visit: Subjects will be scheduled to meet with the study coordinator in the Nutrition and Growth Laboratory at Children's Hospital of Philadelphia. The consent form will be reviewed and signed after all

questions are answered. Subjects will provide information regarding medical history and current medications. Inclusion and exclusion criteria will be reviewed. A urine pregnancy test will be performed. Subjects will undergo a DXA of the hip and spine. If total bone mineral density does not indicate osteoporosis (total BMD in hip or spine equal to or less than -2.5.), we will proceed with additional screening. For those who qualify for the study based on BMD, blood will be drawn for a comprehensive metabolic panel, 25(OH)D, HgbA1c, TSH and FSH and the individual will undergo a pQCT of the tibia. If lab results indicate no evidence of bone disease and that the subject is post-menopausal (FSH greater than 25 mIU/mL), a baseline visit will be scheduled.

Baseline visit: Subjects will undergo MRI scans of the tibia and spine taking 60 minutes. It is possible that a subject will need to return for a repeat MRI scan if the initial scan is unsatisfactory due to technical reasons. Subjects will then be randomized by the device manager to receive an active or placebo Juvent device and will be instructed to stand on the device for a 10 minute period daily. To mask the active/placebo status, all devices are equipped with a small speaker that emits an audible tone. All subjects will be provided with a supply of calcium carbonate and vitamin D3 supplementation. We will dispense 1200 mg/day of calcium carbonate and 1000 IU/day of vitamin D3 in combined form (soft gel, two pills daily) to be taken by all subjects throughout the 12 month duration of the trial.

Randomization and blinding: Subjects meeting the entry criteria at the screening visit will be randomly allocated 1:1 to an active LMMS or a placebo device. The subjects will then be assigned a treatment number. Participant's names and study numbers will be kept in a password-protected database separate from other study records. Random numbers will be generated by a random number generator by the unblinded device manager who will maintain a database with even numbers being assigned to treatment and odd numbers to placebo. This database will not be shared with the PI or other members of the study team before completion of the study. The project manager will be responsible for storing the Juvent devices and the device manager will be responsible for dispensing them to the study staff as determined by the randomization number.

Monitoring of adherence: Data stored on the Juvent devices will be collected by the study team during the six month visit and twelve month visit via a serial connector. The study team will be able to monitor the date, time and duration of each use. The study coordinator will contact subjects bi-weekly to discuss adherence and to provide support.

Six-month visits: Subjects will return to the study site with their Juvent devices. The study team will collect study data from the device via a serial connector. The study team will also review medical status, supplement compliance and to record any adverse events. Additional calcium carbonate/vitamin D3 will be provided if needed.

Twelve-month visit (study completion): Subjects will return to the study site with their Juvent devices. The study team will collect study data from the device via a serial connector. Subjects will return for DXA of hip and spine, pQCT of the tibia and MRI of tibia and spine, as well as a review of medical status, supplement compliance and any adverse events.

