#### Randomization and blinding/unblinding procedures

Subjects meeting the entry criteria at the screening visit will be randomly allocated 1:1 to an active LMMS or a placebo device. The subjects will then be assigned a treatment number. Subjects name and study number will be kept in a password-protected database separate from other study records. Random numbers will be generated by a random number generator by the device manager who will maintain a database with even

numbers being assigned to treatment and odd numbers to placebo. This database will not be shared with the PI or other members of the study team before completion of the study.

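### The protocol prints the key from random number to arm and does not say that blinded staff never see that number; a close to 1:1 split of 83 is, secondarily, not secured

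*Combined protocol and SAP*

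**What the plan says.** Under Study procedures (Randomization and blinding), subjects are to be "randomly allocated 1:1 to an active LMMS or a placebo device". The method follows: "Random numbers will be generated by a random number generator by the unblinded device manager", who keeps a database with "even numbers being assigned to treatment and odd numbers to placebo". The section Randomization and blinding/unblinding procedures repeats both the generator and the parity rule ("Random numbers will be generated by a random number generator by the device manager"; "numbers being assigned to treatment and odd numbers to placebo").

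Three further statements bear on who might see the number:

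- After allocation, "The subjects will then be assigned a treatment number".
- The project manager stores the devices, and the device manager is responsible for "dispensing them to the study staff as determined by the randomization number".
- The device manager's database is withheld from the principal investigator and the rest of the team until the study is complete.

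Subject confidentiality describes a separate subject ID and says that it is the one used for DXA, pQCT and MRI. The target is 83 women randomized to give 64 completers. No section mentions blocks, strata, a balanced list or a limit on imbalance, and none says that the sequence is fixed before enrolment.

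**The concern.** A blind should not depend on nobody noticing a number. Here the key is part of the protocol text, so the last digit of a random number is enough to name the arm. Withholding the database guards the list, but it does not guard a number that has already been seen on a device, a dispensing record or a subject file.

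The people most exposed are those who deal with devices and subjects. Devices are handed to study staff at the start and come back to the team at 6 and 12 months for download. The coordinator phones every subject every two weeks about adherence, follows up those below 80%, and asks about supplements and adverse events. The Outcome analyses section itself treats adherence as decisive for the effect of the device. Encouragement that differed by arm, even unintentionally, is thus a plausible source of bias, as is differential recording of symptoms. Safety Reporting also intends the principal investigator and safety officer to stay blinded unless the safety officer decides otherwise.

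The second issue is balance. A 1:1 ratio is stated, but the only mechanism described is a random number and its parity. Without a restriction, that gives 1:1 on average only.

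**Working it through.** **A. Can the number reach blinded staff?** No arithmetic applies, so the statements are set side by side.

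1. Number to arm: the parity rule, printed in two sections. Anyone who knows the protocol can apply it.
2. Number to device: the device manager dispenses to study staff according to the randomization number. The text does not say what is written on the device or on the record that goes with it.
3. Number to subject: a treatment number is given after allocation. The text does not say whether it is the random number or a different one.
4. Safeguard: the database is withheld. This covers every subject whose number has not been seen elsewhere.
5. Scans: labelled with the subject ID, so a random number is not expected on images.

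Steps 2 and 3 leave a route open, and the safeguard in step 4 does not close it. Step 5 closes it for image reading, on the text as written.

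**B. How far from 1:1 could the arms be?**

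Inputs: 83 randomized, 64 completers, ratio 1:1, all from the protocol. Assumption: independent draws, with even and odd equally likely.

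The plan's own figure: 1 − 64/83 = 22.9% implied attrition. No dropout rate is stated, so 83 cannot be checked against one.

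Arm size follows Binomial(83, 0.5). The difference between arms has SD √83 = 9.1.

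| Event | Probability |
|---|---|
| 41/42, the closest split possible | 17.4% |
| Difference of 9 or more (37/46 or worse) | 38.0% |
| Difference of 11 or more (36/47 or worse) | 27.2% |
| Difference of 17 or more (33/50 or worse) | 7.8% |

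**C. What does imbalance cost?** For a comparison of two means with equal variances, the efficiency of a split a/b relative to an even split is 4ab/N².

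- 36/47: 4 × 36 × 47 / 83² = 6768/6889 = 0.982, a loss of 1.8%.
- 33/50: 4 × 33 × 50 / 83² = 6600/6889 = 0.958, a loss of 4.2%.

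With equal retention, 36/47 leaves 36 × 64/83 = 27.8 and 47 × 64/83 = 36.2 completers, so about 28 and 36 with the total still 64.

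The documents give no effect size, SD or power. Assuming an effect of 0.70 SD (80.0% power at 32/32, two-sided 0.05, normal approximation), power is 79.4% at 28/36, 77.4% at 24/40, and 79.4% averaged over all splits of 64.

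**D. With permuted blocks.** Blocks of 4 (83 = 20 × 4 + 3) or of 6 (83 = 13 × 6 + 5) finish at 41/42. Blocks of 8 (83 = 10 × 8 + 3) finish with a difference of at most 3. If sizes 4, 6 and 8 are mixed, the difference never exceeds half the largest block, which is 4. Because 83 is odd, it is at most 3 at the end.

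**The case against.** The strongest reply is that exposure is conditional and nothing says it will happen. The numbers are generated by an unblinded person and kept in a withheld database. The treatment number is mentioned separately, and dispensing by randomization number may describe only how the device manager picks a device. All of that is a fair reading. It shows that the blind may hold in practice, but not that the protocol secures it.

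Some stronger readings are tempting and are not supported:

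- A reader might infer that image readers would be unblinded. Scans carry the subject ID, so that would need a further breach that the documents do not describe. The primary endpoint is also computed from MRI by finite-element modeling.
- A reader might infer that the withheld database is worthless. One exposed number reveals one woman's arm; the database still protects everyone whose number is unseen.
- A reader might take it as fact that the draws are independent. That is read from silence, and a list balanced in even and odd numbers is not ruled out.
- A reader might conclude that simple randomization is an error. It is a legitimate 1:1 method, and an exact split of 83 is impossible under any scheme.

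Two objections to the remedy also stand in part. Blocking makes later assignments easier to predict if earlier ones become known, which independent draws do not. One unblinded person would still hold the list and dispense the devices, as already planned.

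**Conclusion.** The concern holds as a weakness in concealment and blinding that can be removed at almost no cost. The protocol publishes an arm-revealing rule and leaves open whether blinded staff can see the number to which it applies. The documents do not show that any subject would be unblinded, and the size of any resulting bias cannot be calculated from them.

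Imbalance is secondary. If the draws are independent, a difference of 11 or more has a 27% chance, but the loss is only 1.8% of efficiency at 36/47 and 4.2% at 33/50. Average power falls by about 0.6 percentage points under the assumed 0.70 SD effect. On its own this would not justify a change; it is worth correcting because the same list corrects it. The point should be addressed, but it does not call the trial's validity into question.

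**What to change.** 1. Delete the parity rule from both sections that contain it.
2. Replace it with a 1:1 list generated before first enrolment, in permuted blocks of randomly varying size. Do not give the block sizes in the protocol. The list is held only by the unblinded device manager.
3. Give devices codes, and subjects sequential treatment numbers, that carry no information on the arm. Only the held list links them to treatment.
4. State that blinded staff never see the random number.

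The cost is a short program and a few sentences, with no added staff. Blocking brings slight predictability should assignments become known; the undisclosed, varying block sizes limit it.

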#### Adherence to Study Drugs

##### Supplement Accountability and Handling - Calcium Carbonate and Vitamin D3 Supplementation

We will dispense 1200 mg/day of calcium carbonate and 1000 IU/day of vitamin D3 in combined form (soft gel, two pills daily) to be taken by all subjects throughout the 12 month duration of the trial. Supplements will be purchased by the study project manager. Supplements will be purchased based on availability and price. They will be shipped directly to the Hospital of the University of Pennsylvania. The supplements will be stored in a locked closet in a secured area in the MRI Education center. Only the study coordinator and study project manager will have access to the supplement stock. The dispensing will be conducted by the study coordinator.

At baseline visit each subject will be provided with a six month supply of supplements and asked to take them daily. Subjects will be asked to document any missed supplements by noting this in a journal provided by the study team. As the study coordinator will call each subject bi-weekly to discuss study progress, any concerns or adverse events, subjects will also be asked at this time about supplement compliance. Non-compliant days

will be noted by the study coordinator in the subject's file. At the six month visit subjects will be asked to turn in their supplement bottles. The study coordinator will count and record the amount of pills remaining, if any. All necessary information will be documented on the dispensing and tracking log. Any remaining supplements will be discarded. At the end of this visit the study coordinator will provide each subject with another six month supply of supplements to be taken daily as outlined above. When subjects return for the final 12 month visit they will be asked to turn in their supplement bottles. The study coordinator will count and record the amount of pills remaining, if any. All necessary information will be documented on the dispensing and tracking log. Any remaining supplements will be discarded.

### **Safety issues**

Radiation: This research study involves exposure to radiation from the DXA and pQCT scans and therefore subjects will receive a small radiation dose. This radiation dose is not necessary for medical care and will occur only as a result of participation in the study. At doses much higher than subject will receive, radiation is known to increase the risk of developing cancer after many years. At the doses subject will receive, it is very likely they will see no effects at all.

Blood draw: The blood sampling process infrequently causes pain, bruising, bleeding, vein infection and/or vein clotting at the site, and possible fainting. There is little risk in providing five teaspoons of blood in a healthy individual.

MRI: The known risks associated with MRI are minimal. MRI uses radio waves and a magnetic field to take pictures. The magnet is always on. Some individuals may feel claustrophobic (uncomfortable in small spaces) during the MRI scan or may be disturbed by the sounds of the machine, which are loud and repetitive. Any metal objects on or inside the body may heat up, move and/or not function properly within the scanning room. To minimize any risk from these objects, MRI personnel will screen all subjects. Another risk is that from a metallic object flying through the air toward the magnet and hitting the subject. There are many safety measures in place to reduce this risk, including screening of all persons and materials entering the scanning room. In addition, as the study begins, the door to the room will be closed to minimize the risk of someone accidentally walking into or bringing an object into the magnet room. Some of the pulse sequences and/or RF coils are not FDA approved but are considered to pose no more than minimal risk. It is possible that during the course of the study, the research staff may notice an unexpected finding. Unexpected findings will be considered by the appropriate personnel and the PI will inform the subject if necessary. These possible findings may or may not be significant and may lead to anxiety.

Reproductive risks: Since DXA and pQCT involve radiation, a negative urine pregnancy test will be required before a woman of childbearing potential can participate in this study.

Juvent Vibration Platform: The FDA has designated the risk of the Juvent Vibration Platform as "non-significant".

### **Subject confidentiality**

Subjects will be provided with a study ID, which will consist a unique study number and subject ID (e.g. 9943-001). All patient files will be stored in a locked cabinet in the study coordinator's office. The subject ID will be used for all DXA, p-QCT, and MRI studies.

